11.0 Statistical Considerations

The proposed study is a single-arm phase II clinical trial study in patients with MDS who have failed therapy with hypomethylating agents. The primary endpoint is to determine the overall survival, defined as the time from treatment start to the time of death. A maximum of 80 patients will be accrued at a rate of 1 to 5 patients per month (maximum accrual period 3.33 years). Additional 12 months of follow-up is planned after the last patient is accrued into the trial. It is anticipated that treatment with OM will prolong the

median OS from 4.2 months, as shown in the current standard therapy, to 6 months. The CR, overall survival and toxicity will be monitored during the study, and all data will be used to update the prior distributions for toxicity and efficacy parameters. It will be postulated that the treatment can achieve a CR rate of 20 percent.

We compare median survival time among patients in this study to historical median survival time of 4.2 months. We assume an exponential distribution of failure in the study group and a two-sided significance level of 0.05. Given one additional year of follow up after study recruitment and an accrual rate of 1-5 patients per month, 80 patients will yield a power of 84% to test for a 1.8 months improvement in median survival from 4.2 months.

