11.1 Overall Survival Monitoring

The efficacy endpoint, OS, will be continuously monitored using the Bayesian method by Thall et al.³⁷ Let T_s and T_e represent the OS times for the historical regimen and the experimental regimen OM, respectively. We assume $T_s|M_s$ and $T_e|M_e$ follow an exponential distribution with respective median M_s and M_e . Furthermore, we assume that the prior for M_s follows an inverse gamma distribution $IG(5.0, 16.8)$ to reflect our knowledge of OS in patients treated historically with standard regimen. This prior distribution has a mean of 4.2 months, and a variance of 5.88. The prior for M_e is assumed to be $IG(2.18, 4.94)$, which has the same mean of 4.2 months and a larger variance of 100 to reflect our uncertainty about the median OS of the proposed experimental regimen, OM.

The OS will be continuously monitored, and the study will be terminated early if, based on the available data, there is less than 5% chance that the median OS in patients treated with OM will improve by more than 1.8 months, compared to the historical regimen. The futility stopping rule is as follows:

$$\Pr(\text{Me} > \text{Ms} + 1.8 \text{ months} \mid \text{data}) < 0.05$$

The operating characteristics of this decision rule are summarized in Table 1 using the one-arm TTE software developed by the Department of Biostatistics at M.D. Anderson Cancer Center.

Table 1. Operating characteristics for the design (based on 5000 simulations)

Scenario	True Median (months)	$\Pr(\text{Stopped Early})$	Mean No. patients	Average Trial Duration (months)
1	2.0	0.9999	13	16.26
2	3.0	0.8882	32	22.54
3	4.2	0.2332	66	34.00
4	5.0	0.1088	73	36.29
5	6.0	0.0478	77	37.58
6	7.0	0.0236	78	38.05

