The monitoring for OS will be carried out through the Clinical Trial Conduct (CTC) website (<https://biostatistics.mdanderson.org/ClinicalTrialConduct>) which is housed on a secure server at MDACC and maintained by the MDACC Department of Biostatistics. Access to the website will be gained through usernames and passwords provided by the MDACC Department of Biostatistics. Training on the use of the CTC will be provided by the biostatistical collaborator of the study, with emphasis on the importance of timely updating of follow-up times and recording of events. The monitoring rule for OS will be applied continuously when a new patient is enrolled or an existing patient's data is updated. If the stopping rule is met, an automatic email will be sent out to the study PI, RN and the study statistician to keep them informed and the CTC website will not allow enrollment of any new patients.

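### The OS futility rule in 11.1 (cutoff 0.05, applied continuously) does not produce Table 1: at a 4.2-month median it stops about 45-50% of trials, not 23%

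*Combined protocol and SAP*

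**What the plan says.** Section 11.1 models overall survival as exponential. The historical median Ms has prior IG(5.0, 16.8) and the median on omacetaxine, Me, has prior IG(2.18, 4.94). The trial stops for futility if "there is less than 5% chance that the median OS in patients treated with OM will improve by more than 1.8 months" over the historical regimen. The displayed formula has the same cutoff: Pr(Me > Ms + 1.8 | data) < 0.05.

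The text then states: "The operating characteristics of this decision rule are summarized in Table 1". Table 1, from 5,000 simulations, lists the stopping probability, mean number of patients and trial duration at six true medians.

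On timing: "The monitoring rule for OS will be applied continuously when a new patient is enrolled", or when an existing patient's data change. Once the rule is met, "the CTC website will not allow enrollment of any new patients". Section 11.1 gives no minimum number of patients or cohort size for this rule. Section 11.2 gives both (5 and 5) for the response and toxicity rules.

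Section 11.0 sets a maximum of 80 patients, "accrued at a rate of 1 to 5 patients per month", with 12 months of further follow-up, a target median of 6 months against 4.2, and 84% power.

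**The concern.** The priors, model, margin, cutoff and look schedule are all stated, so Table 1 can be checked apart from the accrual rate. When the rule is simulated, the stopping probabilities come out about twice those tabulated at 4.2 months and about three times those tabulated at 6 months.

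This matters because the rule is binding, enforced by software, and acts on a primary endpoint. Anyone who approved it on the strength of Table 1 was shown the wrong chance of stopping and the wrong expected sample size for the rule in the text. If the website enforces 0.05, a drug that reaches the 6-month target is stopped far more often than the 4.8% shown.

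**Working it through.** **Inputs.** Priors, margin, cutoff and look schedule are from 11.1; 80 patients and 12 months of follow-up are from 11.0. The prior parameters are read as shape a and scale b, with mean b/(a−1) and variance b²/[(a−1)²(a−2)]:

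- Ms: mean 16.8/4 = 4.2; variance 4.2²/3 = 5.88. This agrees with the plan: "This prior distribution has a mean of 4.2 months, and a variance of 5.88".
- Me: mean 4.94/1.18 = 4.19; variance 4.19²/0.18 ≈ 97. The plan gives 4.2 and 100, so the difference is rounding.

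**Accrual rate (assumption).** The plan gives only a range. Table 1 durations follow mean N/3 + 12 months: 16.3, 22.7, 34.0, 36.3, 37.7, 38.0, against 16.26, 22.54, 34.00, 36.29, 37.58, 38.05 listed. So 3 per month is used, and 1 to 5 per month is checked below.

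**Posterior.** With d deaths and total follow-up T months, Me | data ~ IG(2.18 + d, 4.94 + ln2 × T). Pr(Me > Ms + 1.8) is averaged over Ms ~ IG(5, 16.8).

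**Boundary at 0.05.** Stop if T is below:

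| Deaths | 2 | 3 | 5 | 10 | 20 | 40 |
|---|---|---|---|---|---|---|
| T (months) | 3.58 | 7.85 | 16.9 | 41.0 | 91.4 | 194.7 |

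At 40 deaths this is an observed median of ln2 × 194.7/40 = 3.37 months. A check with 2,000,000 random draws at these six points gave probabilities of 0.0497 to 0.0500.

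**Simulation.** Exponential survival, Poisson accrual, looks up to the last enrolment; 100,000 trials per cell (40,000 to 60,000 for monthly looks). Entries are Pr(stop)/mean N.

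| True median | Table 1 | 0.05, enrolments only | 0.05, enrolments and deaths | 0.025, enrolments only | 0.0275, monthly |
|---|---|---|---|---|---|
| 2.0 | 0.9999/13 | 1.000/9.6 | 1.000/8.9 | 1.000/12.4 | 1.000/14.1 |
| 3.0 | 0.888/32 | 0.968/21.2 | 0.974/19.1 | 0.890/31.6 | 0.890/33.3 |
| 4.2 | 0.233/66 | 0.447/52.3 | 0.503/48.1 | 0.248/64.9 | 0.237/66.1 |
| 5.0 | 0.109/73 | 0.234/64.2 | 0.285/60.5 | 0.107/72.8 | 0.099/73.6 |
| 6.0 | 0.048/77 | 0.126/71.0 | 0.164/68.4 | 0.050/76.5 | 0.045/76.9 |
| 7.0 | 0.024/78 | 0.080/74.2 | 0.107/72.3 | 0.029/77.9 | 0.025/78.2 |

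The Monte Carlo standard error of the 0.2332 entry is √(0.2332 × 0.7668/5000) ≈ 0.006. In rows 2-6 the two 0.05 columns miss the tabulated Pr(stop) by 18 to 44 standard errors. The 0.025 column is within 2.4 and the 0.0275 monthly column within 2.3. With looks at enrolments and deaths, 0.02 is within 3.7 and 0.021 within 3.1.

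**Can another setting rescue 0.05?**

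- Accrual of 1 to 5 per month: 0.45-0.51 at 4.2 months and 0.12-0.17 at 6.0.
- Minimum of 10 patients: 0.41-0.46 at 4.2 and 0.08-0.11 at 6.0.
- Monthly looks: 0.410 at 4.2 and 0.103 at 6.0.
- Looks every 10 patients: 0.051 at 6.0, but 0.930 at 3.0 and 0.303 at 4.2.
- Looks every 6 months: 0.235 at 4.2, but mean N is 21 at 2.0 months (table: 13) and Pr(stop) is 0.027 at 6.0.
- Grid of 115 settings (looks every 2 to 40 patients, at enrolments, at enrolments and deaths, or monthly; minimum 1 to 40 patients; some equivalent): the best, every 16 patients, is still 5.7 standard errors off in its worst row, with mean N off by 6.5.

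**Power at 6.0 months, early stop counted as no claim.** Using a two-sided 0.05 log-median test against 4.2 months (0.861 with no rule): 0.735-0.766 at 0.05 with continuous looks, 0.783-0.802 at 0.05 with a 10-patient minimum, and 0.825-0.828 under the settings that come close to Table 1. The loss is about 6-9 points, or 2-4 with the minimum. Section 11.0 names no test, so only these differences are used.

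**Side check.** 0.9999 × 5000 = 4999.5, not a whole count. The other five entries are whole counts: 4441, 1166, 544, 239 and 118.

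**The case against.** The strongest reply is that the rule itself is clear: words and formula agree, it can be run as written, and Table 1 only describes it. If the website holds whatever setting generated Table 1, conduct is unaffected. The rule is for futility only, so no false claim of efficacy follows. All of that stands, and it makes the harm to conduct conditional. It does not remove the contradiction, since in that case the protocol misstates its stopping rule.

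A second reply is that much of the gap comes from the look schedule, and the schedule inside the software is not visible. Survival follow-up after treatment is only every 3 to 6 months (Section 7.0), so looks in practice may be sparser than assumed. Looks every 4 months at 0.05 do come close at medians of 5 to 7 months: 0.115, 0.050 and 0.021. But they give 0.938 at 3.0, 0.294 at 4.2 and a mean N of 17 at 2.0 months, so they still miss Table 1, and they are not the continuous monitoring that 11.1 specifies.

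Three narrower points also stand. The 0.02 cutoff with looks at deaths is only an approximate match. The power figures leave out the response and toxicity rules of 11.2, so they are not the trial's power. The 0.9999 entry changes no decision.

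**Conclusion.** The concern holds. With the stated priors, margin and continuous looks, a 0.05 cutoff gives early stopping of about 0.45-0.50 at 4.2 months (Table 1: 0.233) and 0.13-0.16 at 6.0 months (Table 1: 0.048), with mean N of 48-52 at 4.2 months (Table 1: 66). The lower stopping figures are for looks at enrolments only; the higher ones add looks at deaths.

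This rests on 3 patients per month, no minimum number of patients and prompt data entry. Changing the accrual rate within the planned range does not alter the conclusion, and no minimum or sparser schedule tried at 0.05 matches all six rows. A lower cutoff comes close, but its value depends on the look schedule, and which setting was run cannot be settled from the documents. What is certain is that a binding rule on a primary endpoint and its stated operating characteristics disagree, and they must be reconciled.

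**What to change.** Retrieve the software run behind Table 1, and check the cutoff, look schedule and minimum number of patients loaded in the monitoring website. Then do one of two things:

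- **Correct the text.** Restate in 11.1, in words and formula, the cutoff that generated Table 1. Change the look schedule or add a minimum only if the run shows them.
- **Correct the table.** Keep 0.05 with continuous looks and regenerate Table 1 in the same software. At 3 per month, with looks at enrolments and deaths and no minimum, expect Pr(stop)/mean N of about 1.00/9, 0.97/19, 0.50/48, 0.28/61, 0.16/68 and 0.11/72. Looks at enrolments only give lower stopping probabilities, as in the table above.

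Either way, make the website setting agree with the text, and state the accrual rate, look schedule and any minimum. Correct the 0.9999 entry or the number of simulations. Say whether the 84% power in 11.0 takes futility stopping into account (nothing in 11.0 indicates that it does), and give the power with the chosen rule applied.

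The cost is one retrieved run, one check of the website, and either an edited cutoff or a re-run table. No extra patients are needed.

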11.2. CR Rate and Toxicity Monitoring

Complete response rate and toxicity will be monitored simultaneously using the Bayesian approach of Thall, Simon, Estey (1995, 1996) and the extension by Thall and Sung (1998). This regimen of the experimental treatment will be considered worthy of further investigation if it elicits an increase in CRR to 20% with acceptable toxicity. A toxicity rate greater than 30% is considered unacceptable. Thus, a beta (20, 80) and beta (0.4, 1.6) priors were assumed for the standard treatment response distribution and experimental treatment response prior distribution, respectively. In addition, a beta (30, 70) and beta (0.6, 1.4) priors were assumed for the standard treatment toxicity rate and experimental treatment toxicity prior distribution, respectively. Interim monitoring rules, assuming the prior distributions, were constructed that meet the following two conditions,

- 1) $\Pr(\theta_{S, \text{Toxicity}} < \theta_{E, \text{Toxicity}} | \text{data}) > 0.975$ and,
- 2) $\Pr(\theta_{E, \text{CR}} > \theta_{S, \text{CR}} | \text{data}) < 0.025$

Where $\theta_{E, \text{Toxicity}}$ and $\theta_{E, \text{CRR}}$ are the toxicity and response rates for the experimental treatment, and $\theta_{S, \text{Toxicity}}$ and $\theta_{S, \text{CRR}}$ are the toxicity and response rates for the standard treatment respectively. The first rule provides for stopping the study if excessive toxicity is highly probable (i.e., probability >97.5%) for the experimental treatment. The second condition will stop the study early if the data suggest that it is unlikely (i.e., probability < 2.5%) that CR rate of the experimental treatment is 20%. Assuming the minimum number of patients is 5, the maximum number of patients is 80 and the cohort size is 5. Multc Lean Desktop (version 2.1.0) was used to generate the toxicity and futility stopping boundaries and the OC table (Table 4). The monitoring rule for the toxicity rate, based on these assumptions and monitoring conditions above is in Table 2. Toxicity is defined as grade 3 or higher drug-related non-hematologic toxicity during the first cycle. For example, accrual will cease if 5 patients experience toxicities among the first 5 patients treated or if 7 or more patients experience toxicities among the first 10 patients.

Table 2. Stop accrual if the number of toxicities is greater than or equal to indicated (i.e., # patients with toxicities) among the number of patients evaluated

# patients evaluated	# patients with toxicities	# patients evaluated	# patients with toxicities
5	5	45	22-45
10	7-10	50	24-50
15	9-15	55	26-55
20	11-20	60	28-60
25	14-25	65	30-65
30	16-30	70	32-70
35	18-35	75	34-78
40	20-40	80	Always stop with his many patients

Monitoring the response rate, based on the above assumptions will begin after 5 patients are treated, on an intent-to-treat basis (Table 3). For example, accrual will cease if 0 patients experience a response in the first 10 patients treated.

Table 3. Stop accrual if the number with CR is less than or equal to indicated (i.e., # patients with CR) among the number of patients evaluated							
# patients evaluated	10-20	25-30	35-40	45	50-55	60-65	70
# patients with CR	0	0-1	0-2	0-3	0-4	0-5	0-6

The probability of stopping the study early for low CRRs (i.e., 10%) was higher than 0.70 when toxicity rates were ranged from 20% to 40%. Probabilities of stopping early for high true toxicity rates (i.e., 40%) were 81% when the true CR rate was 10% and 45% when true CRR was 20%.

Table 4. Operating characteristics for simultaneous monitoring response and toxicity rates for patients treated				
True CRR	True Toxicity Rate	True Probability Vector (CRR/Tox, CRR/NoTox, NoCRR/Tox, NoCRR/NoTox)	Probability of Stopping	Average number of patients treated
10%	20%	(0.02, 0.08, 0.18, 0.72)	0.6960	44
10%	30%	(0.03, 0.07, 0.27, 0.63)	0.7076	43
10%	40%	(0.04, 0.06, 0.36, 0.54)	0.8054	36
20%	20%	(0.04, 0.16, 0.16, 0.64)	0.1346	71
20%	30%	(0.06, 0.14, 0.24, 0.56)	0.1676	69
20%	40%	(0.08, 0.12, 0.32, 0.48)	0.4462	57

30%	20%	(0.06, 0.24, 0.14, 0.56)	0.0309	78
30%	30%	(0.09, 0.21, 0.21, 0.49)	0.0679	76
30%	40%	(0.12, 0.18, 0.28, 0.42)	0.3798	61

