2.3 Myelodysplastic Syndrome (MDS)

Twenty-eight patients with MDS or MDS evolved into AML were treated with OM 5 mg/m²/daily by continuous intravenous infusion for 9 days.²² Their median age was 67 years. Seven patients achieved CR, and 1 had a PR, for an overall response rate of 28%. Complete response occurred in 3 of 15 patients with MDS and in 4 of 13 patients with MDS that evolved to AML. Median duration of remission was 7 months. In this study group, induction death was high (13 of 28 patients), mainly because of myelosuppression-related infections. Myelosuppression was prolonged and severe, but other toxicities were mild.²² The dose schedule of OM used in this study of elderly patients was effective but toxic. Lower dose schedules of OM may demonstrate similar efficacy and lower toxicity in MDS.

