5.2 General study treatment plan

The intent of the study design is for all patients to receive up to 12 courses. Treatment will be continued during the duration of the study unless patients exhibit evidence of treatment failure, disease progression, experience an unacceptable toxicity, or the investigator determines that discontinuation of treatment is in the best interest of the patient.

Patients will be treated with study drugs based on a calculation determined from the patient's body surface area (BSA). BSA will be calculated before each cycle and will be based on the patient's height (measured at baseline) and weight (measured each cycle) and will be adjusted downward to "ideal" weight.

"Patients will be instructed to self-administer OM at home and return unused intact drug syringes to be disposed of by the study staff or dropped off to the Investigational Pharmacy. Patients will be given a Research Medication Diary to record the medication taken each day. Patients will be instructed to bring the diary and any unused intact medication syringes with them to all study visits. Any unused drug will be disposed of per institutional standard practice.

5.3 Dose modifications:

Patients will receive their OM treatment every 4-7 weeks:

- a. OM 1.25 mg/m² SQ every 12 hours (+/- 3 hours) for 3 days.

Courses will be repeated every 4-7 weeks. Subsequent courses can be given with modified schedules as detailed below:

- a. Stable or improved MDS with grade 2 or less toxicity: use same dose schedule as previous course.
- b. MDS not improved with grade 2 or less toxicity, increase dose schedule to 4 days of OM if needed.
- c. MDS stable/improved or not improved with grade 3-4 toxicity, give subsequent course with 2 days of OM if clinically indicated; otherwise may take patient off study.
- d. Other modifications in the dose schedule based on response and toxicity of individual patient are allowed if in the patient best interest, after discussion with principal investigator.
- e. Missed doses will not be made up.

In addition, any drug-related, non-hematologic toxicity experienced by a patient should return to \leq grade 2 or the baseline grade before the patient continues treatment.

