10.1 Expedited adverse event reporting

Refer to **Appendix C** for Leukemia-Specific Adverse Event Recording and Reporting Guidelines.

These guidelines serve to bring the Department of Leukemia in compliance with the institutional policy on Reporting of Serious Adverse Events-definition of expected AE-

"All clinical protocols should include a list of the expected and anticipated events or hospitalizations relating to the study treatment" and Guideline for Good Clinical Practice 4.11.1 "All serious adverse events (SAEs) should be reported.

Adverse event is any untoward medical occurrence that may present during treatment with a pharmaceutical product but which does not necessarily have a causal relationship with this treatment.

Adverse drug reaction is a response to a drug which is noxious and unintended and which occurs at doses normally used in man for prophylaxis, diagnosis, or therapy of disease or for the modification of physiologic function.

Assessing causal connections between agents and disease is fundamental to the understanding of adverse drug reactions. In general, a drug may be considered a contributory cause of an adverse event if, had the drug not been administered, 1) the event would not have happened at all, 2) the event would have occurred later than it actually did, or 3) the event would have been less severe.

Adverse Events (AEs) will be evaluated according to current CTC version in each protocol.

Expected events during leukemia therapy are:

1. *Myelosuppression related events (due to disease or leukemia therapy)*
 - a. *febrile or infection episodes not requiring management in the intensive care unit*
 - b. *epistaxis or bleeding except for catastrophic CNS or pulmonary hemorrhage*
 - c. *anemia, neutropenia, lymphopenia, thrombocytopenia, leukopenia, leukocytosis*
2. *Disease related events*
 - a. *symptoms associated with anemia*

- i. *fatigue*
 - ii. *weakness*
 - iii. *shortness of breath*
 - b. *electrolyte abnormalities (sodium, potassium, bicarbonate, CO₂, magnesium)*
 - c. *chemistry abnormalities (LDH, phosphorus, calcium, BUN, protein, albumin, uric acid, alkaline phosphatase, glucose)*
 - d. *coagulation abnormalities*
 - e. *disease specific therapy (induction, maintenance, salvage, or stem cell therapy)*
 - f. *alopecia*
 - g. *bone, joint, or muscle pain*
 - h. *liver function test abnormalities associated with infection or disease progression*
 - i. *disease progression*
- 3. *General therapy related events*

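### The toxicity stopping rule in Section 11.2 can miss excess early death, and the survival and CR rules cover that gap only in part

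*Combined protocol and SAP*

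**What the plan says.** Section 11.2 defines the monitored event: "Toxicity is defined as grade 3 or higher drug-related non-hematologic toxicity during the first cycle". It sets the threshold ("A toxicity rate greater than 30% is considered unacceptable") and gives the priors ("a beta (30, 70) and beta (0.6, 1.4) priors were assumed for the standard treatment toxicity rate" and for the experimental rate). Accrual stops when the posterior probability of excess toxicity passes 97.5%. Looks come every 5 patients up to 80. Tables 2 and 4 rest on this event.

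On the hazard, Section 2.3 reports of the earlier MDS series that "induction death was high (13 of 28 patients), mainly because of myelosuppression-related infections", and describes the other toxicities as mild.

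On classification, the sections point in different directions:
- Section 5.5.2 treats hematologic toxicity as a blood and marrow category and requires no dose action for it in cycle 1.
- Section 9.0, item 3, names significant infection beside drug-related non-hematologic toxicity, not inside it.
- Section 10.1 puts infections that do not need intensive care under "Myelosuppression related events (due to disease or leukemia therapy").
- The same section gives a broad causality test: a drug can be contributory if, without it, the event would have come later or been milder.

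No section says whether a fatal infection during cytopenia is a toxicity event under 11.2.

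Two other rules see deaths. The survival rule (11.1) counts every death from treatment start. The CR rule (11.2) is applied by intention to treat, so a patient who dies early is a non-responder. Section 2.7 promises ongoing review of adverse events without a numerical boundary.

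**The concern.** A safety boundary should respond to the harm that the trial has most reason to expect. Here that harm is death from infection during myelosuppression. Such a death enters the count only if it is judged both drug-related and non-hematologic. In an open-label single-arm trial of patients with advanced disease, both are judgement calls that the protocol does not settle. If most such deaths are put down to disease or marrow failure, the rule stays silent however many occur.

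The survival rule was not built for this. It asks whether median survival can still beat the historical median by 1.8 months, and long follow-up in survivors offsets early deaths. Nor need the CR rule fire: the series in Section 2.3 had 7 CRs in 28 patients (25%) alongside its 13 induction deaths.

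**Working it through.** **1. Reproduce the plan.** With x events in n patients, the experimental rate is Beta(0.6 + x, 1.4 + n − x) and the standard rate is Beta(30, 70). Accrual stops when Pr(experimental > standard) > 0.975. All 15 boundaries in Table 2 reproduce exactly (5/5, 7/10, 9/15, ..., 34/75). With the CR rule built the same way, all nine stopping probabilities in Table 4 reproduce within 0.004 (for example 0.444 against 0.4462).

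**2. Toxicity rule alone.** This is an exact recursion over the looks. P(stop) is 0.03% at a 15% countable rate, 0.2% at 20%, 4% at 30%, 36% at 40% and 74% at 46.4%.

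**3. Dependence on attribution.** Take 13/28 = 46.4% early deaths and an assumed 10% of other countable toxicity. P(stop) by share of deaths counted is:
- none: 0.00
- a quarter: 0.002
- half: 0.05
- three quarters: 0.44
- all: 0.94

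**4. Adding all cycle-1 deaths to the same rule.** The event rate becomes t + (1 − t)e, with toxicity rate t and death rate e assumed independent. For t = 0.15:
- e = 0.25 gives 0.3625 and stops 18%
- e = 0.30 gives 0.405 and stops 39%
- e = 0.464 gives 0.545 and stops 97%

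**5. Background mortality.** Under exponential survival, 28 days is 0.92 months. A median of 4.2 months gives 1 − 2^(−0.92/4.2) = 14%, and a median of 6 months gives 1 − 2^(−0.92/6) = 10%.

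**6. Existing rules together.** After d deaths and T months of total follow-up, the experimental median is IG(2.18 + d, 4.94 + ln2·T), against the historical IG(5.0, 16.8). Accrual of 3 per month follows from Table 1 (66/3 + 12 = 34.0 months, as stated).

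Assumptions of mine: early deaths are spread over month 1; survivors have a median of 6 or 8 months from then; 15% have countable toxicity, with no early death counted; CR is 20% of all patients; survival looks come at each enrolment from the tenth patient. The last column adds an illustrative early-death rule with a 15% limit: priors Beta(15, 85) and Beta(0.3, 1.7), cutoff 0.95.

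| Early death | Existing rules stop (survivor median 6 / 8 months) | With separate death rule |
|---|---|---|
| 10% | 19% / 16% | 19% / 17% |
| 14% | 25% / 19% | 27% / 22% |
| 20% | 38% / 29% | 49% / 44% |
| 25% | 51% / 42% | 75% / 73% |
| 30% | 63% / 53% | 93% / 92% |
| 46% | 96% / 90% | 100% / 100% |

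Simulation error is about 1 point. Starting survival looks at the fifth patient raises the existing-rule range at 20–30% deaths to 35–70%. In the 25% case with an 8-month survivor median, the overall median is 1 + 8·log2(0.75/0.5) = 5.7 months, close to the 6-month target, so the survival rule has little reason to stop. In that case, merely adding deaths to the 30% toxicity rule raises overall stopping from 42% to 48%.

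Alone, the illustrative rule stops 1.4%, 6%, 66% and 90% of trials at 10%, 14%, 25% and 30% deaths.

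**7. Check on the survival reconstruction.** It does not match Table 1. At a 4.2-month median it stops 31–47% of trials, depending on the look schedule, against the stated 23.32%. The existing-rule figures are therefore probably too high. Looks every ten patients come closest to Table 1 and give 24–55% at 20–30% deaths.

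**The case against.** The strongest reply has four parts.

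**Dose.** The 13/28 came from 5 mg/m² × 9 days = 45 mg/m² per course IV, against 1.25 × 2 × 3 = 7.5 mg/m² subcutaneously here, a sixfold difference. Section 2.3 itself suggests less toxicity at lower doses. This stands. A reader might take 46% as the expected rate, but the documents do not support that.

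**Attribution.** A reader might infer from 10.1 that infections are excluded from the count. They are not. The listed item covers only infections that do not need intensive care, the list concerns expectedness for reporting, and the causality test in the same section would often favour counting a fatal infection. This also stands. What is left is an unstated classification, so the rule *can* miss these deaths; it is not shown that it *will*. The 0.03% is the extreme in which none is counted.

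**Other rules.** A reader might conclude that nothing formal responds to early death. The survival rule runs continuously and blocks enrolment, and the CR rule counts early deaths as failures. If CR is 20% among survivors only, the CR rule contributes more: the survival and CR rules together then stop 54–67% of trials at 25% deaths and 67–79% at 30%. This stands in part. The backstop is strong at 46% and partial at 20–30%.

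**Later courses.** Section 5.3 allows a later course to "increase dose schedule to 4 days of OM if needed", and a reader might want the first such course counted against Table 2. That does not fit. Table 2 is a per-patient boundary for one cycle, and a second window for a selected subset changes the event rate and the timing. Limiting the boundary to cycle 1 is a design choice. Individual dose rules, removal criteria and survival monitoring continue afterwards, and a later-course boundary would need its own derivation.

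**Conclusion.** The concern holds as a gap in the toxicity rule, not as an absence of safety monitoring. The only numerical toxicity boundary depends on attribution and classification that the protocol leaves open, for the type of event that dominated its own MDS series. The gap matters most at moderate excess mortality. At 20–30% early death, roughly twice the 10–14% background, the existing rules together stop about 30–70% of trials. At 46% they stop about 90% or more. The figures rest on accrual of 3 per month, survivor medians of 6–8 months, 15% countable toxicity, a 20% CR rate and no early death counted as toxicity. They probably flatter the existing rules, because the survival reconstruction stops more often than Table 1. The documents give no early-death rate for the present regimen in this population, so the size is conditional on scenarios and is not a prediction.

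**What to change.** Keep the Table 2 rule for drug-related toxicity unchanged. Add to 11.2 a separate Bayesian boundary for death from any cause during cycle 1, built in the same software with the same 5-patient looks, and report its operating characteristics beside Table 4, alone and jointly with the survival, CR and toxicity rules. The sponsor chooses the limit, above the background in step 5; the 15% used here is only an illustration.

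State the window in days. Section 2.6 has 28-day cycles but Section 5.3 allows 4–7 weeks. Over 49 days (1.61 months) the same formula gives 17–23% background mortality, so limit and window must be set together. Also state in 11.2 how a fatal infection during cytopenia is classified for the toxicity count.

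The cost is small: one paragraph, one boundary table and a rerun of the operating characteristics. Deaths and their dates are already collected for survival monitoring. The downside is that some deaths from disease will be counted. With the illustrative limit, overall stopping rises by less than 1 point at 10% early deaths and by about 2 points at 14%. Any boundary for later courses should be considered separately, with its own limit.
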